Title: A feasibility pilot study for a social support intervention in kidney transplant candidates

NCT Number: NCT04363515

Date: October 1, 2024

Title:A feasibility pilot study for a social support intervention in
kidney transplant candidates

Drug or Device Not applicable Name(s):

FDA IND/IDE Not applicable

Sponsor: University of Minnesota Clinical and Translational Science Institute

Protocol Date: June 15, 2019

Revision Date(s): Not applicable

Study Principal Investigato1 · (if multicenter study): [name], MS [name] [contact] email: [contact]

Site Principal Investigator: [name], MS

Hennepin Healthcare [name] [contact] email: [contact]

Other Investigators:

PROTOCOL SYNOPSIS

Study Title	Development of a social support intervention for kidney transplant candidates		
Funder	University of Minnesota WERC award		
Clinical Phase	Not applicable		
Study Rationale	Intensive home-based group counseling with a psychologist are the only interventions that have been shown to increase rates of living kidney donation however, they are not feasible for transplant centers. A recent review on strategies to increase living kidney donation concluded that strategies directed at candidates and their social supp01t networks are the most promising based on the data available. Therefore, we propose an intervention that incorporates individualized risk communication into group counseling with patients and their support networks at the transplant center.		
Study Objective(s)	Primary		
	• To determine whether counseling with the shared decision aid, provided in the clinical setting to candidates along with members of their social suppolt network, increases pursuit of transplant.		
	Secondary		
	 To determine whether the intervention influences patient knowledge about kidney transplant, decisional conflict, and hope. To determine if the intervention influences social suppolt group knowledge about kidney transplant and intertion/mativation to 		
	knowledge about kidney transplant and intention/motivation to support the patient through the transplant process.		
Test Article(s) (If Applicable)	Not applicable		
Study Design	Pilot randomized control trial		
Subject Population Key Criteria for Inclusion and Exclusion:	Inclusion criteria include adult kidney transplant candidates at the University of Minnesota or Hennepin County Medical Center. Exclusion criteria include inability to consent, non-English speaking, or candidates for combined organ transplant.		
Number Of Subjects	Total Number of Subjects: 60		
	Total Number of Sites: 2		
Study Duration	Each subject's participation will last 3 months.		
	The entire study is expected to last through November 1 st 2020.		
Study Phases	(1) Screening : screening for eligibility and obtaining consent		

Screening	(2) Intervention: group counseling session	
Intervention		
Follow-Up		
Efficacy Evaluations	Primary evaluation measurements that will be used to assess the efficacy of the intervention	
Pharmacokinetic Evaluations	Not applicable	
Safety Evaluations	Not applicable	
Statistical And Analytic Plan	A Student's T-test will compare means for the primaiy outcome of the number of inquiries per candidate (primary outcome). Chi- squai ed and Student's T-tests will be used to compare secondary outcomes.	
Data And Safety Monitoring Plan	The principle investigator is responsible for data quality management and ongoing assessment of safety.	

page1v

Study Phase	Screening	Treatment/Intervention	Follow-up
Visit Number	1	2	NIA
Informed Consent/Assent	Х		
Review Inclusion/Exclusion Criteria	Х		
Bassline Survey to measure secondru.y outcomes	Х		
Demographics/Medical Histo1y	Х		
Randomization	X		
Intelvention (group counselling session)		X	
Survey to measure secondru.y outcomes		X	
Assess primru.y outcome through medical records			Х

TABLE 1: SCHEDULE OF STUDY PROCEDURES

1 BACKGROUND INFORMATION AND RATIONALE

1.1 Name and Description of Investigational Product or Intervention

We will conduct a pilot randomized trial to compare group counseling with transplant candidates and their suppolt networks that incorporates the shared decision aid with a risk calculator, versus usual pre-transplant care.

1.2 Findings from Non-Clinical and Clinical Studies

Not applicable

1.2.1 Non-Clinical Studies

Not applicable

1.2.2 Clinical Studies

1.2.2.1 Human Pharmacokinetics

Not applicable

1.2.2.2 Clinical Studies in Adults

1.2.2.3 Clinical Studies in Children

1.3 Selection of Drugs and Dosages

Not applicable

1.4 Relevant References

1.5 Compliance Statement

This study will be conducted in full accordance of all applicable Hennepin Healthcare Research Policies and Procedures and all applicable Federal and State laws and regulations. All episodes of noncompliance will be documented and repo1ted according to the Prompt Repo1ting Guidelines, Attachment EEE, of the Hennepin Healthcare IRB Policies and Procedures.

The investigators will perfonn the study in accordance with this protocol, will obtain consent, unless waiver of consent or other alteration is approved, and will repolt unanticipated problems involving risks to subjects or others and SAEs in accordance with The Hennepin Healthcare IRB Policies and Procedures and all Federal requirements. Collection, recording, and rep01ting of data will be accurate and will ensure the privacy, health, and welfare of research subjects during and after the study.

2 STUDY OBJECTIVES

The pmpose of the study is to detennine whether counseling with the shared decision aid, provided in the clinical setting to candidates along with members of their social suppol1 network, increases pursuit of transplant.

2.1 Primary Objective (or Aim)

The primary objective of this study is to detennine whether counseling with the shared decision aid, provided in the clinical setting to candidates along with members of their social suppolt network, increases pursuit of transplant.

2.2 Secondary Objectives (or Aim)

The secondaiy objectives are to:

- Determine whether the intervention influences patient knowledge about kidney transplant, decreases decisional conflict, and hope.
- Detemline if the intervention influences social suppolt group knowledge about kidney transplant and intention/motivation to suppolt the patient through the transplant process.

3 INVESTIGATIONAL PLAN

3.1 General Schema of Study Design

3.1.1 Screening Phase and Baseline Assessment

Potential subjects will be screened using the protocol inclusion and exclusion criteria. Potential subjects will be reached out to over the phone before their initial appointment at the clinic to see if they express interest in hearing more about the intervention. Those whom want to learn more about the intervention will then be met with during their first kidney transplant counseling appointment at the transplant clinic. Permission (info1med consent) will be obtained during this appointment, if the patient would like the participate in the intervention. After the patient has completed the health assessment phase and is officially a candidate for transplant, they will be emolled in the study.

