3.2 Allocation to Groups and Blinding

The enrolled study participants will be randomized via computer into either the intervention or control group. Palticipant and researcher blinding is not feasible for the intervention, but asceltainment and statistical analysis of outcomes will be performed by an analyst blinded to group assignment.

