3.3 Study Duration, Enrollment and Number of Sites

3.3.1 Duration of Study Participation

The study duration per subject will be up to 3 months. There will be one day of screening and one day that the intelvention takes place. The remainder of the time is allotted for patients to undergo standard pre-transplant care and counseling.

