9.6 Informed Consent/Assent and IDPAA Authorization

Informed consent will be obtained by members of the study. The consent process will be documented in writing with the long form of consent documentation. Patients will be called prior to their transplant elgibility screening appointment and asked if they would be interested in hearing more about the intervention. If the patient is interested, informed consent will be obtained during their appointment at the clinic. Members of the study team will obtain concent. Patients will give concent for intervention participation.

We will read the consent document with the participant, beginning with a concise and focused presentation of key infolmation to assist the subject to understand the reasons why one might or might not want to palticipate in the research. We will explain the details in such a way that the participant understands what it would be like to take part in the research study. The intervention will only begin after patients have gone through the screening process and been identified as candidates for kidney transplant, weeks after informed concent is obtained.

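### Table 1 puts randomisation at the one-day screening visit with consent, but sections 3.1.1 and 3.2 together put it after candidacy is confirmed

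*Protocol*

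**What the plan says.** The schedule and the text describe different sequences. (Odd spellings in the quotes come from text extraction and are not part of the point.)

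- **Table 1** has one Screening column, numbered Visit 1. It marks "Informed Consent/Assent", the criteria review, "Bassline Survey to measure secondru.y outcomes", demographics and "Randomization" there. The group session is Visit 2.
- **Section 3.3.1** treats screening as a single day: "There will be one day of screening and one day that the intelvention takes place".
- **Section 3.1.1** places consent at the first transplant counselling appointment: "Permission (info1med consent) will be obtained during this appointment". Enrolment comes later: "After the patient has completed the health assessment phase and is officially a candidate for transplant, they will be emolled in the study".
- **Section 3.2** states who is randomised: "The enrolled study participants will be randomized via computer into either the intervention or control group".
- **Section 9.6** has the intervention begin only once patients have been "identified as candidates for kidney transplant, weeks after informed concent is obtained". Section 9.5 also starts it only after candidacy is established.
- **Section 3.5.1** makes being a kidney transplant candidate inclusion criterion 2. **Section 3.5.2** bars enrolment of anyone who fails a criterion.
- **Sections 4.1 and 4.2.1** place the surveys differently again. Section 4.1 lists only consent and record review at screening. Section 4.2.1 puts the demographic and evaluative surveys at a Visit 1 under Study Intervention, although Table 1 numbers the intervention visit 2.

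**The concern.** Table 1 is what staff at the two sites would work from. Read literally, it has a patient consent, complete the baseline survey and be allocated on the same day, before the health assessment has shown whether the patient is a candidate.

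Two things would be at stake.

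- **Comparability of the arms.** Sections 3.2 and 9.1.2 say that participants and researchers are not blinded. If allocation comes before the health assessment, a patient who knows the assigned arm might be more or less likely to complete that assessment. Losses between allocation and candidacy could then differ by arm. The blinded analyst in section 3.2 cannot undo that. No section says how a randomised patient who is later not accepted as a candidate would be handled.
- **What the pilot measures.** Section 6.3 gives feasibility as the main goal. Any retention figure needs a clear denominator. If patients are randomised before candidacy is known, those who were never eligible are counted with those who left the study.

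**Working it through.** The point concerns the order of procedures. The protocol states no figure to reproduce, and its sample size is not based on power.

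**Step 1: set the two sequences side by side.**

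| Event | Table 1 with 3.3.1 | 3.1.1 with 3.2 and 9.6 |
|---|---|---|
| Consent | Visit 1 | First counselling appointment |
| Candidacy (criterion 2) | Criteria review at Visit 1 | After the health assessment |
| Enrolment | Not shown separately | After candidacy |
| Randomisation | Visit 1 | After enrolment, so after candidacy |
| Intervention | Visit 2 | After candidacy, weeks after consent |

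**Step 2: check whether both can be followed.** Table 1 puts consent and randomisation in one visit, and section 3.3.1 makes that visit one day, so randomisation falls on the day of consent. Section 3.1.1 puts a health assessment phase between consent and enrolment, and section 3.2 randomises those already enrolled, so randomisation falls after that phase. The two agree only if the assessment ends on the day of consent. Nothing says that it does, and the delay of weeks in section 9.6 before the intervention can begin points the other way.

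**Step 3: illustrate the size.** Let q be the share of consented patients who never become candidates. The documents do not give q; 10-40% is an assumption made only to show scale. With N patients randomised at Visit 1, the expected number of non-candidates is N × q, and the chance of at least one is 1 − (1 − q)^N, treating patients as independent. N is 7 + 8 = 15 under section 3.3.2 or 60 under section 6.4. Those two sections disagree, which is a separate matter, so both are shown.

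| q (assumed) | Expected of 15 | Chance of at least one of 15 | Expected of 60 |
|---|---|---|---|
| 10% | 1.5 | 1 − 0.9^15 = 79% | 6 |
| 20% | 3.0 | 1 − 0.8^15 = 97% | 12 |
| 30% | 4.5 | 1 − 0.7^15 = 99.5% | 18 |
| 40% | 6.0 | 1 − 0.6^15 > 99.9% | 24 |

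**Step 4: repeat under the text's sequence.** If randomisation follows confirmed candidacy, no one is allocated while candidacy is undecided, and the expected number of randomised non-candidates is 0 for every q.

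**The case against.** The best defence is that Screening in Table 1 names a phase, not a day. Table 1 is organised by study phase, the heading of section 3.1.1 calls this the screening phase, and sections 9.5 and 9.6 describe a screening process that ends in candidacy. The randomisation mark could then mean the end of that phase, and Table 1 gives no order within the column. This would resolve the conflict, but it does not fit the single visit number or the one day in section 3.3.1.

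Other parts of the defence stand, and they rule out several stronger readings that a reader might infer.

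- **That the trial will randomise ineligible patients.** Sections 3.1.1, 3.2 and 3.5.2 all point away from this. It follows only if a site puts Table 1 above them, and even then eligibility would be undetermined at allocation, not known to be absent. Nothing suggests that the two sites would act differently.
- **That section 3.2 by itself restricts randomisation to confirmed candidates.** It refers only to enrolled participants. The restriction comes from reading it with section 3.1.1.
- **That candidacy is settled weeks after consent.** In section 9.6 the delay applies to the start of the intervention. The gap from consent to candidacy is not stated, and neither is the point from which the three months of participation run. The share of follow-up used up by the assessment therefore cannot be calculated.
- **That an early baseline survey biases the comparison of arms.** Both arms receive usual counselling (section 3.1.2), so its effect enters the change scores of both. Section 5.2.1 asks only that baseline precede the intervention, and either timing meets that.

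The protocol also says that it is a feasibility pilot not powered to test anything. That lowers the stakes for efficacy, but not for a clear retention denominator.

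**Conclusion.** The contradiction holds. Table 1 with section 3.3.1 places randomisation on the day of consent; sections 3.1.1 and 3.2 together place it after candidacy is confirmed. The harm is conditional: if a site follows Table 1 literally, patients are openly allocated before criterion 2 can be assessed, some may be lost afterwards, possibly unequally by arm, and retention would mix screen failures with dropout.

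The size is unknown because the documents give no non-candidacy rate. The range of 1.5-6 of 15 patients, or 6-24 of 60, rests wholly on the assumed 10-40%. With planned arms of 7 and 8, though, even one or two such losses would be noticeable.

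**What to change.** Split the Table 1 Screening column in two:

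- (a) first appointment: consent and record review;
- (b) after candidacy is confirmed: final eligibility check, baseline survey, then randomisation, in that order and in both arms.

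Then bring the other sections into line. Section 3.3.1 should no longer describe screening as one day. Sections 4.1 and 4.2.1 should place the surveys where Table 1 does and use the same visit numbers. Section 3.2 should say outright that randomisation follows confirmed candidacy. Consented patients who never become candidates should be reported as screen failures before randomisation, separately from losses after it.

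This follows the sequence already in sections 3.1.1 and 3.2 and adds no patients. It is not purely a change of wording: the baseline survey moves to a later contact in both arms, and the protocol would need to say how that contact is made.

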3.1.2 Study Intervention

Participants in the intervention group first undergo usual pre-transplant counseling, and will then undergo a group counseling session with members of their suppmt network at the transplant center. The session will include 1) a description of general options for treatment of end stage kidney disease, 2) the likely outcome of each of those options specific to the transplant candidate utilizing the decision aid, 3) a presentation of common reasons to pursue or not pursue each of those options (including common barriers to living donation), and 4) a discussion of how the suppolt network can be involved in the transplant process. Tllis discussion will be infolmed by focus groups conducted in a previous study. The group counseling session will follow a general script and will be facilitated by the principal investigator or a trained transplant educator, with recording and random review of the sessions to ensure quality and consistency of the content. Printed results of the decision aid output will be shared with the clinical transplant team to replicate clinical practice.

The control group will undergo the usual pre-transplant counseling and clinical evaluation conducted by the transplant center team. The control group will be info1med about the availability of the online shared decision aid by a member of the research team.

3.1.3 Part 2 (Use an appropriate descriptor such as "Open-Label Treatment")

Not applicable

3.1.4 Follow-up

Not applicable

3.2 Allocation to Groups and Blinding

The enrolled study participants will be randomized via computer into either the intervention or control group. Palticipant and researcher blinding is not feasible for the intervention, but asceltainment and statistical analysis of outcomes will be performed by an analyst blinded to group assignment.

3.3 Study Duration, Enrollment and Number of Sites

3.3.1 Duration of Study Participation

The study duration per subject will be up to 3 months. There will be one day of screening and one day that the intelvention takes place. The remainder of the time is allotted for patients to undergo standard pre-transplant care and counseling.

3.3.2 Total Number of Study Sites/Total Number of Subjects Projected

The study will be conducted at two investigative sites in the United States.

Recruitment will stop when approximately 60 subjects are consented (7 patients in the control group + 8 patients + 6-7 friends and family each in the intelvention group).

3.4 Study Population

3.4.1 Use of Vulnerable Populations and Patients Who Opt Out of Research

Vulnerable populations and patients who opt out will not be included in the study.

3.5 Inclusion and Exclusion Criteria

3.5.1 Inclusion Criteria

- l) Adult males or females.
- 2) Kidney transplant candidates.

3) Additional criteria as required.

3.5.2 Exclusion Criteria

- 1) Non-English speaking individuals.
- 2) Individuals with impaired ability to consent.
- 3) Candidates for combined organ tTansplant.
- 4) Patients who choose to opt out of research.

Subjects that do not meet all of the enrollment criteria may not be enrolled. Any violations of these criteria must be repolted in accordance with IRB Policies and Procedmes.

4 STUDY PROCEDURES

4.1 Screening Visit and Baseline Assessment

- Info1med Consent
- Medical Record Review

4.2 Study Intervention

4.2.1 Visit 1

- Demographic survey
- Evaluative survey

4.2.2 Visit 2 and Visit 3

Not applicable

4.3 Part 2 of the Study (e.g. Open-Label Treatment)

Not applicable

4.3.1 Visit 4

Not applicable

4.3.2 Visit 5

Not applicable

4.4 Follow-up

• Medical records

4.4.1 Visit 6

Not applicable

4.4.2 Visit 6: End of Study

Not applicable

4.5 Unscheduled Visits

Not applicable

4.6 Concomitant Medication

Not applicable

4.7 Rescue Medication Administration

Not applicable

4.8 Subject Completion/Withdrawal

Participants may withdraw from the study any time without prejudice of their care. The infmmed consent document stipulates that we will retain data collected prior to study withdrawal. Paltial withdrawal (no further active paiticipation but with ongoing data collection after withdrawal from health record) will be requested if a participant wishes to cease palticipation, as per the informed consent document.

4.8.1 Early Termination Study Visit

Subject's data from after withdrawal from the study will be not be used.

5 STUDY EVALUATIONS AND MEASUREMENTS

- Informed Consent: infmmed consent will be used to infmm patients about the intelvention and their rights if they choose to participate.
- Medical Record Review: medical records will be reviewed to ensure that patients meet inclusion/exclusion criteria for intervention. They will also be used during follow-up to assess our primary outcome variable, to determine if the patient engaged in pursuit of transplant.
- Demographic survey (see appendix): This survey will be used to understand the population participating in the intervention.
- Evaluative survey (see appendix): This survey will assess our secondary outcome measures, to determine whether the intervention influences patient knowledge about kidney transplant, decisional conflict, and hope. Also, to determine if the intervention influences social support group knowledge about kidney transplant and intention/motivation to suppmt the patient through the transplant process.

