6 STATISTICAL CONSIDERATIONS

The sample size (n=60) will be sufficient for conducting statistical analysis of the intervention. A Student's T-test will compare means for the primaly outcome of the number of inquiries per candidate. Both a Chi-squared and Student's T-tests will be used to compare secondaly outcomes.

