6.1 Primary Endpoint

Prima1y endpoint: pursuit of transplant

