6.3 Statistical Methods

A Student's T-test will compare means for the primaly outcome of the number of inquiries per candidate between and within the intervention and control groups. Both a Chi-squared and Student's T-tests will be used to compare secondruy outcomes between and within the intervention and control groups. This is a feasibility pilot study; therefore, it is not powered to test anything. We will be collecting data that we could adjust for (i.e. demographics), but we will not be adjusting, because the main goal of this particulru study is to gauge if the intervention is feasible.

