6.3.2 Efficacy Analysis

The primaly efficacy endpoint will be the change in pursuit of transplant between the baseline and the outcome evaluation. Secondary endpoints will include the change in patient knowledge about kidney transplant, patient decisional conflict, patient hope, social supp01t group knowledge about kidney transplant and social support group intention/motivation to support the patient through the transplant process between the baseline and outcome evaluation. All measurements will be compared with the control/no treatment group measurements.

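### The primary outcome is tested as a count of inquiries, but its assigned source, the medical record, is described as showing only whether the patient pursued transplant

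*Protocol*

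**What the plan says.** **What is tested.** Section 6 and the synopsis name the primary "outcome of the number of inquiries per candidate". The method in section 6.3, a two-sample comparison by Student's test, is meant to "compare means for the primaly outcome of the number of inquiries per candidate between and within the intervention and control groups". This is a count, analysed on the scale of the mean.

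**What the endpoint is called.** Section 6.1 gives only "Prima1y endpoint: pursuit of transplant", with no event or unit. Section 6.3.2 says the primary efficacy "endpoint will be the change in pursuit of transplant between the baseline and the outcome evaluation".

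**Where it comes from.** Table 1 has the primary outcome assessed from medical records, in the follow-up column only. Section 4.4 lists medical records as the sole follow-up procedure. Section 5 says of the records: "They will also be used during follow-up to assess our primary outcome variable, to determine if the patient engaged in pursuit of transplant". The same section gives the evaluative survey the secondary outcomes. Section 5.2, however, includes pursuit of transplant among the efficacy measures, and 5.2.1 says the baseline and outcome surveys carry the measures listed there.

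**What differs by arm.** Under section 3.1.2, intervention candidates attend a group session with their supporters at the transplant center. For that arm, "Printed results of the decision aid output will be shared with the clinical transplant team to replicate clinical practice". Controls are told only that the online aid exists. Section 3.3.2 counts "8 patients + 6-7 friends and family each in the intelvention group" and lists no friends or family for controls. Section 3.2 has outcomes ascertained and analysed by an analyst blinded to group.

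**The concern.** A count, a yes/no status and a change from baseline are three different variables. The protocol assigns a source to the primary outcome but describes that source as giving the second, while the test is on the first. It never says who makes an inquiry, to whom, or how repeat contacts are counted. Two abstractors could follow the protocol faithfully and return different numbers for the same candidate.

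The arms also differ in how much supporters come into contact with the center as part of the study itself. With no rule separating study-session contacts from inquiries, part of the between-arm difference could reflect what was written down, or what was counted, and not what supporters or candidates went on to do. The blinded analyst does not remove this, because the difference would arise when the record was made, before abstraction.

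**Working it through.** The protocol gives no inquiry rate, effect size or record completeness, so there is no stated figure to reproduce. The check is mainly a comparison of sections.

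**1. The variable, section by section**

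| Place | Form of the primary outcome |
|---|---|
| Synopsis, 6, 6.3 | Count per candidate, means compared |
| 5 | Whether the patient engaged in pursuit (yes/no wording) |
| 6.1 | Named, with no unit |
| 6.3.2 | Change from baseline to outcome evaluation |

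**2. Is an inquiry item listed anywhere?** Section 5.1.1 lists record and questionnaire variables; none is an inquiry. That list is for screening and baseline, so it is weak evidence alone. In the appendix, patient survey items 1-9 test knowledge, 10-13 ask about certainty in the decision, 14-25 about outlook, and 26 about completing forms. Family survey items 1-9 repeat the knowledge questions, 10 concerns coping, 11-12 intention to help, and 13 completing forms. No item asks about inquiries made or steps taken toward transplant. Section 5.2's implication that the surveys measure pursuit is therefore not borne out, and medical records remain the only working source.

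**3. Is there a baseline value?** Table 1 schedules the primary outcome at follow-up only. The change in 6.3.2, and the within-group comparison in 6.3, have no scheduled baseline measurement.

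**4. How far apart can count and yes/no be?** Assume Poisson counts, so P(any inquiry) = 1 - exp(-mean). The means below are assumptions, each a doubling.

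- Means 1 and 2: 1 - exp(-1) = 0.632; 1 - exp(-2) = 0.865.
- Means 2 and 4: 0.865 and 0.982.
- Means 3 and 6: 0.950 and 0.998.

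The same doubling of the count can be plain or nearly invisible in the yes/no version.

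**5. Recording by arm, purely as illustration.** Let c0 and c1 be the shares of inquiries recorded in control and intervention. With equal true means, the apparent ratio of means is c1/c0. The rejection rates come from 20,000 simulated trials per case: Poisson counts, true means of 1, 2 and 4, two-sided 5% Student's t-test, 7 control and 8 intervention patients (section 3.3.2), no true effect. The capture shares and the test level are assumptions.

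| c0 / c1 | Apparent ratio | Rejection rate |
|---|---|---|
| Equal (50%, 80% or 100%) | 1.00 | 0.042-0.050 |
| 60% / 80% | 0.80/0.60 = 1.33 | 0.06-0.13 |
| 50% / 90% | 0.90/0.50 = 1.80 | 0.11-0.39 |
| 80% / 60% | 0.60/0.80 = 0.75 | 0.07-0.14 |

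Equal but partial recording creates no spurious difference and leaves the ratio of means intact. It does shrink the difference in means, which is what the t-test compares: true means of 2 and 4 recorded at 50% become 1 and 2, so the difference falls from 2 to 1. Unequal recording would bias the comparison, in either direction.

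**The case against.** The strongest reply has four parts.

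- **Nothing in the protocol describes how complete the records are in either arm.** This stands. A reader might infer that capture is partial and favours the intervention arm, but that is not established. The decision-aid printout is shared to mirror practice, and no section links it to charting of inquiries. Questions answered in the session could equally reduce later recorded contacts. More contact by supporters may also be a real effect and not an artefact.
- **Inquiries may be the candidate's own.** Section 5 speaks of the patient's engagement, and the primary objective does not mention donors. On that reading the candidate's record is a natural source. Medical records might also include a center contact log. Both are possible, and the protocol settles neither, which supports asking for a definition.
- **This is a pilot.** Sections 6.3 and 6.4 say it is not powered for any test, and 6.3 makes feasibility the main goal. That limits the weight of any false-positive rate. It does not excuse the mismatch: the primary objective in 2.1 is still whether counseling increases pursuit, and a between-arm test is planned.
- **Abstraction rules may sit in a statistical analysis plan not shown here.** Fair for detailed rules. But the protocol itself gives conflicting forms of the variable and a source that does not match the tested one, and those statements need reconciling where they stand.

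**Conclusion.** The point holds in a limited form. The tested variable is a count. The only working source is described in yes/no terms, one section makes the endpoint a change with no scheduled baseline, and another implies a survey measure that does not exist. These are checkable from the text and need no assumption.

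Differential recording is a risk of unknown size and direction. It rests on supporters attending a center session, and decision-aid output reaching the clinical team, in one arm only, with no rule on whether session contacts count. Blinded ascertainment would not correct it. The figures in the illustration depend wholly on assumed means and capture shares and estimate nothing about this trial.

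A reader might also infer that control-arm inquirers are unreachable, because friends and family are listed only for the intervention arm and the HIPAA waiver in 9.6.3 is marked not applicable. The documents do not support this. No section proposes reading inquirers' own records, and section 9.6 says only that "Patients will give concent for intervention participation", so it is not clear that supporters' records would be authorised in either arm.

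This should be corrected, because it determines how the primary outcome is measured.

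**What to change.** In section 5, section 4.4, Table 1 and sections 6.1 to 6.3.2:

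- State one primary variable: the count of inquiries per candidate over the follow-up period. Align the yes/no wording in section 5, the change from baseline in 6.3.2 and the listing in 5.2 with it.
- Say who makes an inquiry and to whom.
- Name one source, read identically in both arms. An example is the transplant center's own record of contacts about a named candidate, if one exists, released as a de-identified count per study ID. The protocol does not mention such a record, so each site must confirm that it is kept.
- State that contacts made only to arrange or attend the study session are not counted.

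The cost is a wording change and one data request per site. Excluding session contacts may lower the intervention-arm count.
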